**Protocol Revision History**

|                                 |                   |
|---------------------------------|-------------------|
| Initial Approval Version | 03/12/2015 |
| Amendment #1 Version     | 05/15/2015 |
| Amendment #2 Version     | 10/07/2015 |
| Amendment #3 Version     | 07/05/2016 |
| Amendment #4 Version     | 09/16/2016 |
| Amendment #5 Version     | 07/11/2017 |

## Phase I/II Study Combining Tosedostat with Capecitabine in Patients with Advanced or Metastatic Pancreatic Adenocarcinoma

### SCHEMA

| Dose De-Escalation Schedule |                                        |                                        |
|------------------------------------|----------------------------------------|----------------------------------------|
| Dose Level                  | Tosedostat (PO daily) Days 1-21 | Capecitabine (PO BID) Days 1-14 |
| Level 0
(Starting dose)         | 120 mg                                 | 1000 mg/m                  |
| Level -1                           | 60 mg                                  |                                        |

## Glossary of Abbreviations

|            |                                                                  |
|------------|------------------------------------------------------------------|
| AE         | Adverse event                                                    |
| ALT (SGPT) | Alanine transaminase (serum glutamate pyruvic transaminase)      |
| AML        | Acute myeloid leukemia                                           |
| ANC        | Absolute neutrophil count                                        |
| AST (SGOT) | Aspartate transaminase (serum glutamic oxaloacetic transaminase) |
| B-HCG      | Beta human chorionic gonadotropin                                |
| BID        | Bis in die (twice a day)                                         |
| BSC        | Best supportive care                                             |
| CBC        | Complete blood count                                             |
| CFR        | Code of Federal Regulations                                      |
| CIVI       | Continuous IV infusion                                           |
| CMP        | Complete metabolic panel                                         |
| CR         | Complete response                                                |
| CRF        | Case report form                                                 |
| CRP        | C-reactive protein                                               |
| CT         | Computed tomography                                              |
| CTCAE      | Common Terminology Criteria for Adverse Events                   |
| CTEP       | Cancer Therapy Evaluation Program                                |
| DLTs       | Dose Limiting Toxicities                                         |
| DNA        | deoxyribonucleic acid                                            |
| DPD        | Dihydropyrimidine dehydrogenase                                  |
| DSM        | Data and Safety Monitoring                                       |
| ECG        | Electrocardiogram                                                |
| ECOG       | Eastern Cooperative Oncology Group                               |
| EDTA       | ethylenediaminetetraacetic acid                                  |
| FDA        | Food and Drug Administration                                     |
| FFPE       | Formalin-fixed paraffin-embedded                                 |
| FWA        | Federal wide assurance                                           |
| HIV        | Human Immunodeficiency Virus                                     |
| HRPO       | Human Research Protection Office (IRB)                           |
| IND        | Investigational New Drug                                         |
| IRB        | Institutional Review Board                                       |
| IULN       | Institutional upper limit of normal                              |
| IV         | Intravenous                                                      |
| KPS        | Karnofsky performance score                                      |
| LVEF       | Left ventricular ejection fraction                               |
| MM         | Multiple myeloma                                                 |
| mOS        | Median overall survival                                          |
| MRI        | Magnetic resonance imaging                                       |
| MTD        | Maximum tolerated dose                                           |

|        |                                                          |
|--------|----------------------------------------------------------|
| MUGA   | Multi-gated acquisition scan                             |
| NCCN   | National Cancer Center Network                           |
| NCI    | National Cancer Institute                                |
| NIH    | National Institutes of Health                            |
| NSCLC  | Non-small cell lung cancer                               |
| OHRP   | Office of Human Research Protections                     |
| ORR    | Overall response rate                                    |
| OS     | Overall survival                                         |
| PD     | Progressive disease                                      |
| PFS    | Progression-free survival                                |
| PI     | Principal investigator                                   |
| PK     | Pharmacokinetic                                          |
| PO     | Per os (by mouth)                                        |
| PR     | Partial response                                         |
| QASMC  | Quality Assurance and Safety Monitoring Committee        |
| RECIST | Response Evaluation Criteria in Solid Tumors (Committee) |
| RNA    | Ribonucleic acid                                         |
| RP2D   | Recommended phase II dose                                |
| rt-PCR | Reverse transcriptase polymerase chain reaction          |
| SAE    | Serious adverse event                                    |
| SCC    | Siteman Cancer Center                                    |
| SD     | Stable disease                                           |
| TTP    | Time to progression                                      |
| UPN    | Unique patient number                                    |

## **1.0 BACKGROUND AND RATIONALE**

### **1.1 Metastatic Pancreatic Adenocarcinoma**

Metastatic pancreatic adenocarcinoma has a dismal prognosis, with a median overall survival of less than one year (1). According to the American Cancer Society, there were an estimated 45,220 new cases of pancreatic cancer in 2013 with 38,460 deaths (1). Despite comprising only 3% of all new cancer diagnoses, pancreatic cancer remains the fourth most common cause of cancer death, and it is expected to rise to the second most common cause of death by 2030. Unfortunately, pancreatic cancers are typically diagnosed at advanced stages when the only available treatments are palliative; around 40% of patients are found to have metastatic disease at the time of diagnosis. Recent advances using combination chemotherapies have extended the overall survival (OS) of patients with metastatic disease, but only by about 6 months (to one year) (2), still making pancreatic adenocarcinoma one of the most deadly solid malignancies.

### **1.2 First-Line Therapy for Inoperable or Metastatic Pancreatic Adenocarcinoma**

For over 40 years, until the approval of gemcitabine in 1997, fluorouracil-based chemotherapy was the mainstay of treatment for pancreatic adenocarcinoma despite mean survival rates of less than 6 months (3). Gemcitabine was approved after it was shown to be superior to 5-FU in terms of clinical benefit. In a randomized controlled trial (4), 126 patients with advanced pancreatic cancer were randomized to receive either gemcitabine at 1000 mg/m^2 weekly for 7 weeks followed by one week off, then on Days 1, 8, and 15 of a 28-day cycle, or weekly 5-FU at 600 mg/m^2. The primary endpoint in this trial was clinical benefit, which was defined by pain score, Karnofsky performance score (KPS), and body weight. Not only did patients receiving gemcitabine have a better clinical benefit rate (23.8% vs. 4.2%; p=0.0022), but gemcitabine-treated patients had a statistically better median overall survival (mOS) (5.65 vs. 4.41 months; p=0.0025) and overall one year survival rate (18% vs. 2%; p=0.0025).

Combining gemcitabine with nab-paclitaxel (nanoparticle albumin bound paclitaxel) improved overall survival compared to gemcitabine alone. In a phase III randomized, open-label, multicenter trial (MPACT), 861 untreated patients with metastatic pancreatic cancer were randomized to receive gemcitabine plus nab-paclitaxel or gemcitabine alone (5). mOS, progression-free survival (PFS), and tumor response rates were significantly improved in the combination group compared to gemcitabine alone (8.5 vs. 6.7 months, p<0.001; 5.5 vs. 3.7 months, p<0.001; 23% vs 7%, p<0.001, respectively).

In 2011, combination chemotherapy with drugs other than gemcitabine in metastatic pancreatic cancer also showed a meaningful survival benefit over single agent gemcitabine (2). The ACCORD phase II/III trial studied 342 patients with previously untreated metastatic pancreatic cancer who were randomized to receive FOLFIRINOX (14-day cycles of 5-FU at 400 mg/m^2 on Day 1 followed by 2400 mg/m^2 CIVI over 46 hours, leucovorin at 400 mg/m^2 on Day 1, irinotecan at 180 mg/m^2 on Day 1, and

oxaliplatin at 85 mg/m^2 on Day 1) or gemcitabine alone (1000 mg/m^2 given weekly for 7 weeks followed by one week off, then on Days 1, 8, and 15 of a 28-day cycle). Patients treated with FOLFIRINOX had a significantly improved mOS of 11.1 months compared with 6.8 months in the gemcitabine arm (p<0.001), as well as an improved PFS of 6.4 months compared to 3.3 months (p<0.001). A higher tumor response rate was seen in the FOLFIRINOX arm as well (31.6% vs 9.4%; p<0.001). FOLFIRINOX is now considered one of the standard first-line regimens for patients with metastatic pancreatic cancer and good performance status.

[figure not shown]
[figure not shown]
### **1.3 Second-line Therapy for Inoperable or Metastatic Pancreatic Adenocarcinoma**

Despite the aggressive nature of pancreatic cancer, nearly half of the patients who have progressed on front-line therapy are able to receive second-line therapy. A fluorouracil-based regimen is currently recommended for patients who progress through a gemcitabine-based regimen. In a phase III clinical trial, patients who had progressed on a gemcitabine-based chemotherapy were randomized to receive folinic acid at 200 mg/m^2 5-FU at 2000 mg/m^2 as a continuous 24 hour infusion on Days 1, 8, 15, and 22, and oxaliplatin at 850 mg/m^2 on Days 8 and 22 of a 42-day cycle (OFF regimen), or best supportive care (BSC) (6). The study was terminated early due to low recruitment, but despite this, the OFF regimen showed a median survival of 4.82 versus 2.30 months (p=0.008) and a mOS survival benefit of 9.09 versus 7.90 months (p=0.031) in patients treated with OFF compared to BSC. However, recently the results of the CONKO-003 trial were published, which was a randomized, open-label phase III trial in which 168 patients with advanced pancreatic cancer who had progressed on gemcitabine were randomized to folinic acid and fluorouracil (FF) or oxaliplatin and FF (OFF) (7). Median overall survival was significantly longer in the OFF group compared to FF alone (5.9 versus 3.3 months, p=0.010). PFS was also extended in the OFF treatment arm compared to the FF arm (2.9 versus 2.0 months, p=0.019). Based on these trials, the National Comprehensive Cancer Network (NCCN) recommends fluoropyrimidine plus oxaliplatin as one of the second-line treatment options.

However, for patients who performance status is poor, a fluoropyrimidine alone is often given, either as infusional 5-FU or capecitabine, and it is considered to be a reasonable second line option endorsed by the NCCN. 5-FU is a fluorinated pyrimidine that acts as an antimetabolite antineoplastic agent. Capecitabine is an orally administered prodrug of 5'-deoxy-5-fluorouridine which generates 5-FU selectively in tumor cells, and so is often used instead of 5-FU given its ease of administration. Both are frequently used as the control group in the second-line setting in clinical trials. For example, three recent phase II and phase III trials have used capecitabine or 5-fluorouracil in combination with an investigational drug compared with capecitabine or 5-fluorouracil alone. A phase II randomized, double-blind, placebo-controlled trial of ruxolitinib, a JAK1/JAK2 inhibitor, in combination with capecitabine in patients with recurrent or metastatic pancreatic cancer (RECAP trial) showed improved OS in patients with an elevated C-reactive protein (CRP). The hazard ratio (HR) for OS in the intent to treat population was 0.79 [95% CI, 0.53-1.18; P=0.25 (2-sided)] and in the pre-specified subgroup analysis in

patients with an elevated CRP, the HR for OS was 0.47 (95% CI: 0.26-0.85;  $P=0.01$  (2-sided)), with 6-month survival in the ruxolitinib arm of 42% vs. 11% in the placebo arm (8). And, as mentioned above, 5-FU was used as the control arm in the CONKO-003 trial. Finally, in a phase III trial of MM-398 (NAPOLI-1 trial), patients were randomized to receive MM-398, 5-FU, or combination therapy (9). Median OS was 6.1 months in the combination arm compared to 4.2 months in the 5-FU arm (HR 0.67,  $p=0.012$ ).

#### 1.4 Tosedostat

#### 1.4 Study Rationale

Unresectable advanced or metastatic pancreatic adenocarcinoma is an incurable disease, with a mean overall survival of less than one year despite current available treatments. The two most common first-line chemotherapies for pancreatic adenocarcinoma are FOLFIRINOX (2) or gemcitabine plus nab-paclitaxel (5). However, most patients will progress on these regimens. Many patients cannot tolerate FOLFIRINOX due to significant adverse side effects, making gemcitabine plus nab-paclitaxel a frequent first-line choice. And although 5-FU and capecitabine have activity in pancreatic cancer, their use as a single agent generally only gives an overall survival benefit of a few months. Therefore, one treatment strategy is to improve the efficacy of capecitabine with an additional chemotherapeutic agent.

*APN/CD13* is a zinc metalloprotease and has been investigated in pancreatic cancer (19). Reverse transcriptase polymerase chain reaction (rt-PCR) was performed on 50 tumor samples in patients who underwent pancreatectomy between 1992 and 1999, to quantify the expression of this gene in pancreatic cancer. Of the 50 tumors tested, 24 (48%) were positive by immunohistochemistry and 25 (50%) were positive for gene expression of *APN/CD13* by rt-PCR. There was a correlation between *APN/CD13* expression and overall survival. Patients whose tumors were positive for *APN/CD13* expression had a shorter overall survival than in patients whose tumors were negative, 9.5 versus 13.2 months respectively,  $p=0.0009$ ). Multivariate analysis of the 50 patients showed that *APN/CD13* expression was a significant independent prognostic factor ( $p=0.016$ ).

Given the evidence of possible upregulation of metalloproteases and their potential prognostic values in pancreatic cancer, the study rationale is to combine tosedostat with capecitabine, a standard second-line chemotherapy. We chose tosedostat at 120 mg daily as the first dose level for the following reasons. In the phase I study using tosedostat as a single agent, the MTD was determined to be 240 mg in patients with solid tumors (17). However, in patients with acute myeloid leukemia or multiple myeloma (20), the MTD

## **1.5 Correlative Studies Background**

Please refer to Section 9.2.

## **2.0 OBJECTIVES**

### **2.1 Primary Objectives**

1. Phase I: To determine the recommended phase II dose (RP2D) and dose-limiting toxicities (DLTs) of tosedostat and capecitabine combination therapy in patients with advanced or metastatic pancreatic cancer.
2. Phase II: To determine progression-free survival (PFS) rate at 3 months of tosedostat and capecitabine combination therapy in patients with advanced or metastatic pancreatic cancer.

### **2.2 Secondary Objectives**

1. To determine the overall response rate (ORR) of patients with advanced or metastatic pancreatic cancer being treated with tosedostat and capecitabine combination therapy.
2. To determine the time-to-progression (TTP) of patients with advanced or metastatic pancreatic cancer being treated with tosedostat and capecitabine combination therapy.
3. To determine overall survival (OS) of patients with advanced or metastatic pancreatic cancer being treated with tosedostat and capecitabine combination therapy.
4. To determine CA19-9 response of patients with advanced or metastatic pancreatic cancer being treated with tosedostat and capecitabine combination therapy.

## 2.3 Exploratory Objectives

1. To explore the predictive molecular biomarkers for treatment response in patients with advanced or metastatic pancreatic cancer being treated with tosedostat and capecitabine combination therapy.
2. To explore the prognostic biomarkers for patients with advanced or metastatic pancreatic cancer receiving tosedostat and capecitabine combination therapy.
3. To correlate genetic alterations with response to treatment with combination tosedostat and capecitabine in patients with advanced or metastatic pancreatic cancer.

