### **9.2.3 Evaluation of genetic alternations that potentially associated with treatment response**

Pancreatic cancer, as all human malignancies, is caused by genetic mutations. Mutations in *KRAS*, *P16*, *TP53* and *SMAD4* genes are common (1821). With the advent of improved sequencing techniques, the identification of several key genetic alterations has led to the development of targeted therapies, such as imatinib and numerous EGFR-targeted therapies (cetuximab, erlotinib). Identifying the key genetic alterations in pancreatic cancer may lead to a better understanding of carcinogenesis and the development of more effective therapies. It is also important to analyze the somatic mutations and correlate them with treatment response and overall survival as there may be certain genetic alterations that prove to be more chemosensitive to certain drugs than others.

The Genomics and Pathology Service at Washington University (GPS@WU) offers next-generation sequencing of tumor somatic mutations in 42 oncogenes, tumor suppressors, and other cancer genes. The rationale for performing next generation sequencing is to identify the key genetic alterations in each patient's tumor. This information can then be used to compare patients' clinical information to see if there is a correlation between response rates, overall survival, and specific genetic mutations.

Next generation sequencing is performed on all coding regions of ABL1, AKT1, ALK, APC, ASXL1, ATM, BRAF, CEBPA, CTNNB1, DNMT3A, ERBB2, EGFR, ESR1, FGFR4, FLT3, IDH1, IDH2, JAK2, KIT, KRAS, MAPK1(ERK), MAP2K2(MEK), MET, KMT2A(MLL), MPL, MYC, MYD88, NOTCH1, NPM1, NRAS, PDGFRA, PIK3CA, PTEN, PTPN11, RB1, RET, RUNX1, STK11, TET2, TP53, VHL and WT1 to detect single nucleotide variants and small insertions and deletions; selected introns of ALK and KMT2A(MLL) to

detect rearrangements. Next generation sequencing will be performed on initial tumor biopsies.

A GPS requisition form is obtained and completed from the Washington University Genomics and Pathology Services

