**Target lesions:** All measurable lesions up to a maximum of 2 lesions per organ and 5 lesions in total, representative of all involved organs, should be identified as target lesions and recorded and measured at baseline. Target lesions should be selected on the basis of their size (lesions with the longest diameter), be representative of all involved organs, but in addition should be those that lend themselves to reproducible repeated measurements. It may be the case that, on occasion, the largest lesion does not lend itself to reproducible measurement in which circumstance the next largest lesion which can be measured reproducibly should be selected. A sum of the diameters (longest for non-nodal lesions, short axis for nodal lesions) for all target lesions will be calculated and reported as the baseline sum diameters. If lymph nodes are to be included in the sum, then only the short axis is added into the sum. The baseline sum diameters will be used as reference to further characterize any objective tumor regression in the measurable dimension of the disease.

**Non-target lesions:** All other lesions (or sites of disease) including any measurable lesions over and above the 5 target lesions should be identified as non-target lesions and should also be recorded at baseline. Measurements of these lesions are not required, but the presence, absence, or in rare cases unequivocal progression of each should be noted throughout follow-up.

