## **14.0 STATISTICAL CONSIDERATIONS**

### **14.1 Sample Size**

In the phase I part of the study, a de-escalation 3+3 design is used to determine the recommended phase II dose of tosedostat when combined with capecitabine in patients with advanced or metastatic pancreatic adenocarcinoma. The minimal number of patients needed for the phase I part of the study is 6 patients assuming no DLT is observed in Dose Level 1. The maximal number of patients is 12 patients.

For the phase II part of the study, the primary endpoint of the study is to assess the progression-free survival (PFS) of the combination therapy. Based on historical data, the PFS of 2.0 months was observed with either 5-FU or capecitabine in the second-line setting, so a median PFS of 4 months for the combination regimen would be considered clinically meaningful for further development. With a sample size of 36 patients including 3-6 patients from the phase I portion, the study has power 0.80 to identify an increase of the median PFS (2.0 to 4.0 months) at a 0.05 significance level, assuming 12 months of accrual and 6 months of follow-up. We will consider this phase II part as a pilot study for the PFS as endpoint; therefore a sample size of 36 is adequate. We expect to enroll 3-4 patients per month; therefore it is feasible to recruit 36 patients within 1 year.

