### **14.2 Data Analysis**

PFS and OS will be estimated by Kaplan-Meier product limit method. The progression-

free survival and overall survival probabilities at certain time points (e.g. 3 months, 6 months) will be presented as well. The overall response rate (ORR) and CA19-9 response will be characterized by summary statistics (frequency and proportion). The logistic regression model will be considered to explore the predictive molecular biomarkers, the prognostic biomarkers for treatment response, and to investigate the correlation between genetic alterations and response to treatment.

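### Section 14.2 names only a logistic model, with no sparse-data version, to relate a 42-gene panel to response in at most 36 patients; odds ratios will often have no finite estimate

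*Combined protocol and SAP*

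**What the plan says.** Section 2.3 lists three exploratory objectives. The first concerns predictive molecular biomarkers for treatment response. The third is "To correlate genetic alterations with response to treatment with combination tosedostat and capecitabine in patients with advanced or metastatic pancreatic cancer".

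The only analysis text for them is one sentence in section 14.2, which begins "The logistic regression model will be considered to explore the predictive molecular biomarkers, the prognostic biomarkers for treatment response" and goes on to genetic alterations and response. It gives no penalised or exact version, no test statistic, no rule for empty cells, no minimum number of mutated tumors and no multiplicity rule. It does not say which response is meant. The sentence before it covers two candidates: "The overall response rate (ORR) and CA19-9 response will be characterized by summary statistics (frequency and proportion".

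Section 9.2.3 sets the number of markers: the genomics service "offers next-generation sequencing of tumor somatic mutations in 42 oncogenes, tumor suppressors, and other cancer genes". Section 14.1 sets the number of patients, on PFS alone: "With a sample size of 36 patients including 3-6 patients from the phase I portion". The study calendar (section 10.0) asks for archival tissue only where it is available, so the genetic analysis set may be smaller than 36.

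**The concern.** Logistic regression of a yes/no response on a yes/no marker has a finite maximum-likelihood odds ratio only if all four cells of the 2x2 table are occupied. With few responders, that often fails. The estimate then runs to infinity (or is undefined, if there are no responders or no mutated tumors), the standard error becomes very large, and the Wald p-value printed by default goes to about 1. A table in which every responder carries the mutation is one of these cases.

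What is at stake is how the exploratory results can be read. If default output were tabulated across 42 genes, many rows would hold unusable estimates, and a p-value near 1 could be taken as evidence of no association. The primary PFS conclusion is not affected.

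**Working it through.** **Plan's own figure.** There is none to reproduce. The documents give no responder count, response rate, gene prevalence or power for the biomarker analysis.

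**Inputs**
- n = 36 at most (14.1); n = 24 is used as an illustration of missing tissue.
- 42 genes (9.2.3).
- Response rate: an assumption. The only single-agent rates in the documents are first-line gemcitabine: 7% (section 1.2, "23% vs 7%, p<0.001, respectively") and 9.4% (the FOLFIRINOX comparison, also 1.2). These give 36 × 0.07 = 2.5 and 36 × 0.094 = 3.4 responders. A range of 5% to 20% gives 1.8 to 7.2.
- Gene prevalence: not stated, so 10%, 20% and 50% are shown.

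**Step 1: chance of an empty cell for an unassociated gene.** With response rate o, prevalence p and R responders:

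P(empty) = 1 − Σ(R = 1 to n−1) Bin(R; n, o) × [1 − p^R − (1−p)^R] × [1 − p^(n−R) − (1−p)^(n−R)]

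For exactly 3 responders of 36:
- p = 0.1: 1 − (1 − 0.001 − 0.729) × (1 − 0.0309) = 0.74
- p = 0.2: 1 − (1 − 0.008 − 0.512) × (1 − 0.0006) = 0.52
- p = 0.5: 1 − (1 − 0.125 − 0.125) = 0.25

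Averaged over a random number of responders:

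| n | Response rate | p = 10% | p = 20% | p = 50% |
|---|---|---|---|---|
| 36 | 7% | 81% | 65% | 48% |
| 36 | 10% | 72% | 51% | 29% |
| 36 | 20% | 51% | 23% | 4% |
| 24 | 10% | 83% | 67% | 50% |

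These include trials with no responder at all: 0.93^36 = 7% at a 7% rate and 0.90^36 = 2% at 10%, with n = 36.

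**Step 2: what the output looks like.** Take 3 responders of 36, all among 4 mutated tumors (3/4 versus 0/32).
- Ordinary fit: standard error about 14,000, Wald p = 0.999.
- Fisher's exact: C(4,3)/C(36,3) = 4/7140 = 0.0006.
- Likelihood ratio of the same ordinary model: log-likelihood 3 ln 0.75 + ln 0.25 = −2.249 with the marker and 3 ln(3/36) + 33 ln(33/36) = −10.326 without. Twice the difference is 16.15 on 1 df, p = 0.00006.
- Firth point estimate, which for a 2x2 table adds one half to each cell: (3.5 × 32.5)/(1.5 × 0.5) = 152. It is large and imprecise, but finite.

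**Step 3: limit of the Wald test.** Over all tables with 3 responders of 36 and no empty cell, the smallest Wald p-value is 0.0089. It can never reach 0.05/42 = 0.0012.

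**The case against.** A reader might infer that the planned model misses even near-perfect markers, so that objectives 1 and 3 cannot be answered. The documents do not support that. The failure belongs to the Wald p-value, and section 14.2 names no test. For a marker present in 90% of responders and 5% of non-responders, with 3 responders of 36, power at 0.05 is 0.19 by Wald but 0.97 by the likelihood-ratio test of the same ordinary model, 0.97 by Firth penalised likelihood ratio and 0.95 by Fisher. An analyst who looked at the 2x2 table would also see the separation.

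Other parts of the opposing case also stand:
- Section 14.2 commits only to considering a logistic model. Unpenalised, gene-by-gene fitting is the natural reading, but it is not written.
- About 3 responders is not a figure from the documents. If response meant CA19-9 response, there could be more events.
- The objectives are exploratory and 14.1 calls phase II a pilot for PFS. Unadjusted testing is usual in such work. Even so, 42 independent tests at a true 5% level would give up to 1 − 0.95^42 = 88% chance of at least one false positive, so the number of genes tested should be reported.

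It is also tempting to replace response with best percent change in target-lesion sum, since 12.2 already provides that "The baseline sum diameters will be used as reference to further characterize any objective tumor regression in the measurable dimension of the disease". Under an illustrative normal model (1 SD shift, n = 36, wild-type response 5-10%), a rank test does have more power: 0.58-0.60 against 0.38-0.44 for the likelihood-ratio test at 20% prevalence. At 0.05/42, however, the rank test falls to 0.11-0.12. Percent change also answers a different question from the one in section 2.3, and the model ignores new lesions and missing scans.

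What remains is that the likelihood-ratio test rescues the p-value but not the estimate. The odds ratio is still infinite with no usable Wald interval, and the plan says nothing about either.

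**Conclusion.** The point holds as a gap in specification. Section 14.2 names one method that, in its default form, will often give no finite estimate in this sample. At an assumed tumor response of 7-10%, that means about half to four fifths of fits for unassociated genes at 10-20% prevalence, and 29-48% at 50% prevalence. At 20% response it remains common for infrequent mutations (51% at 10% prevalence) but is rare at 50% prevalence (4%). Fewer tissue samples make it worse.

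The size depends on an assumed response rate, assumed prevalences, no true association, and response meaning tumor response. The gap itself does not: neither the outcome nor the sparse-data method is stated. It bears on how the exploratory results can be interpreted. It does not show that strong associations would go undetected by every test of the model.

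**What to change.** In section 14.2, for exploratory objectives 1 and 3:
1. State that response means RECIST response as assessed under section 12.4.
2. Use Firth-penalised logistic regression with penalised-likelihood intervals and p-values, or Fisher's exact test, in place of ordinary maximum likelihood with Wald inference.
3. Report the results as hypothesis-generating and give the number of genes tested.
4. Optionally, add a rank test on best percent change in the target-lesion sum as a supportive analysis, not as a replacement for response.

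The cost is a few sentences and a little more analysis work. No new data are needed: response is already assessed, and the tumor measurement form (section 11.0) already collects lesion sizes at baseline, after every even-numbered cycle and at end of treatment.
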